Despite the tremendous burden experienced by patients undergoing HCT and their caregivers, studies of interventions to improve their QOL and reduce distress are lacking.^{7,11,19-21} Involvement of specialty-trained palliative care clinicians in the care of patients with advanced solid tumors has been shown to improve patient's QOL and mood and reduce their caregiver's psychological distress.²²⁻²⁷ Consequently, the early integration of palliative and oncology care is becoming the standard of care for patients with advanced solid tumors.²⁸ However, palliative care is rarely consulted to assist in the management of patients with hematologic malignancies.²⁹⁻³¹ Misconceptions equating palliative care with end-of-life care have contributed to the lack of involvement of palliative care for patients undergoing potentially curative therapy with HCT.²⁹⁻³³ However, given their extensive training and expertise in managing complex symptoms, palliative care clinicians are ideally positioned to treat the challenging toxicities experienced by this population.

We completed a single center randomized trial of inpatient integrated palliative and transplant care versus transplant care alone in patients with hematologic malignancies undergoing HCT (see Preliminary Studies).³⁴ Palliative care clinicians followed patients throughout their transplant hospitalization and conducted a minimum of two visits per week to 1) address patients' physical and psychological symptoms; 2) manage patients' and caregivers' expectations; and 3) provide both patients and caregivers with strategies to cope with the patients' illness and health status. Patients randomized to receive palliative care had a significant improvement in their QOL, symptom burden, depression, and anxiety during their hospitalization compared to those randomized to transplant care alone. Notably, the effects of the intervention were sustained three and six months post-HCT with significant improvements in depression, and post-traumatic stress symptoms.^{34,35} Caregivers also reported improvements in their coping and depression symptoms.³⁴ This was the first trial to establish the feasibility and preliminary efficacy of integrated palliative and transplant care in improving outcomes for patients with hematologic malignancies and their caregivers.

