8.3 Exploratory endpoints

- Compare patient coping (Brief Cope) between the study groups

PROTOCOL TITLE: Multi-Site Randomized Trial of Inpatient Palliative Care for Patients with Hematologic Malignancies Undergoing Hematopoietic Stem Cell Transplantation

- Compare caregiver coping (Brief Cope) between the study groups
- Assess whether group differences in patient-reported QOL (FACT-BMT) are mediated by improved symptom burden (mediator: ESAS/HADS), or coping (mediator: Brief Cope)
- Assess whether patient or transplant related characteristics are moderators of the impact of palliative care intervention on patient-reported QOL

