Study staff will administer self-report study assessments at baseline, week-2 during the transplant hospitalization (+ 2 day window), at three, six, and twelve months post-HCT (+/- 2 week window). If the patient prefers verbal administration of the assessment, the study staff member will be someone blinded to the intervention assignment. The demographic questionnaire, included in the patient and caregiver baseline assessments only, will ask study participants to provide their email address to allow us to email study assessments to those who do not have a scheduled appointment within the follow-up time points. If patients do not have an email address, we will either send them paper copies of the survey or ask them to complete them verbally over the telephone. We will track the methods of survey completion among participants. The entire study assessment battery will be administered at all time points (except demographics) and takes approximately 20 minutes to complete. The selected self-report measures have strong psychometric properties and have been well validated in previous studies in this population. All study measures are available in both English and Spanish.

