Participants will use tablet computers to complete questionnaires during hospitalization or in clinic. If any participants refuse or are unable to complete the questionnaires on the computer, they will be permitted to use hard-copy paper versions. Participating caregivers who are not present in the hospital during the period of data collection will be provided with remote access to the REDCap system [Appendix L], paper-based questionnaires for home administration [Appendix K], or administration of questionnaire over the phone [Appendix M]. The RA will contact patients (in person), and caregivers (in person or via telephone) daily for two days to remind them to complete and return the surveys. If study participants fail to complete the surveys within two days of the expected time point, we will report the data as missing and document the reason for incompleteness. Table 4 details the schedule for administering the self-report measures. All participants (patients and caregivers) will complete baseline evaluation within 72 hours of study enrollment (excluding public holidays, in which case the RA will approach in 96 hours). All participants will then have a second evaluation during their second week of hospitalization for HCT. Patients undergoing autologous HSCT (and their caregivers) will have their second evaluation during the hospitalization on day +5 (48 hour window: day +5 to day +7). Patients undergoing allogeneic HCT (and their caregivers) will have their second evaluation during the hospitalization on day +8 (48 hour window: day +8 to day +10). We have chosen these time points carefully to assess patients during their hospitalization at the peak of severity in symptoms based on the type of transplant being performed. All patients (and caregivers) will also complete additional questionnaires at 3, 6, and 12 months post-transplantation (+/- 2 week window).

Table 4: Administration of Self-Report Measures

Participant	Baseline	Week-2:(Day+5 auto, day +8 allo)	3, 6, & 12 months (+/- 2 week window)
Patient Measures:			
Demographics	X		
FACT-BMT/Fatigue	X	X	X
ESAS	X	X	X
HADS	X	X	X
PHQ-9	X	X	X
PCL (PTSD)	X	X	X
Brief Cope	X	X	X
Caregiver Measures:			
Demographics	X		
CarGOQOL (QOL)	X	X	X
HADS	X	X	X
PHQ-9	X	X	X
Brief Cope	X	X	X

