10.0 Data and Specimen Banking: Not applicable

10.1 Data analysis

Specific Aim 1: To demonstrate the efficacy of inpatient integrated palliative and transplant care for improving patient-reported outcomes: Analyses will begin with descriptive and graphical summaries of the endpoints and evaluation of whether a normality assumption is reasonable for the endpoint or whether transformation is necessary. All statistical tests will be two-sided with an alpha level of 0.05. For all secondary and exploratory outcomes, we will use the false discovery rate (FDR) control method to address the issue of multiple testing. We selected an FDR of 0.15, which denotes the acceptable percentage of results that potentially represent false positives.⁶² The primary endpoint of the study will be to compare patient QOL (FACT-BMT) scores at week-2 between the study groups controlling for baseline values and demographic and clinical factors (as necessary for any imbalances in baseline variables) using a linear regression model. We will also compare secondary endpoints including patients' symptoms (ESAS), fatigue (FACT-Fatigue), depression and anxiety symptoms (HADS and PHQ9), and coping (Brief Cope) at week-2 between the study groups using linear regression models controlling for baseline values and clinical factors (as necessary for any imbalances in baseline variables). In the event that the effect of the intervention differs by transplant type, conditioning intensity, or other patient characteristics, we will examine these variables as interaction terms in the linear regression analyses. Finally, we will compute the effect size and Reliability Change Index to assess practical and clinical significance in the degree of change in the primary and secondary outcomes.

We will also utilize linear mixed models of the longitudinal data, allowing us to account for dependency among means over time and to control for demographic and clinical factors (as necessary for any imbalances in baseline variables) when examining change between groups in outcomes of interest across multiple time points (i.e., baseline, 2 weeks, 3, 6, and 12 months post-HCT). We will estimate practical and clinical significance of these outcomes (Cohen's d and Reliability Change Index).

Specific Aim 2: To assess the impact of inpatient integrated palliative and transplant care on caregiver-reported QOL and psychological outcomes: We will similarly compare caregivers' QOL

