PROTOCOL TITLE: Multi-Site Randomized Trial of Inpatient Palliative Care for Patients with Hematologic Malignancies Undergoing Hematopoietic Stem Cell Transplantation

(CARGOQOL), depression and anxiety symptoms (caregivers HADS and PHQ9), and coping at week-2 using linear regression models controlling for baseline values and clinical factors (as necessary for any imbalances in baseline variables). We will also use linear mixed models of the longitudinal data, allowing us to account for dependency among means over time and to control for demographic and clinical factors (as necessary for any imbalances in baseline variables) when examining change between groups in outcomes of interest across multiple time points (i.e., baseline, 2 weeks, 3, 6, and 12 months post-HCT). We will again estimate practical and clinical significance of these outcomes (using Cohen's d and Reliability Change Index).

Specific Aim 3: To explore mediators and moderators of the effect of the palliative care intervention on patient-reported QOL: We will conduct bootstrapped tests of mediation to determine whether group differences in patient-reported QOL (FACT-BMT) are mediated by improved symptom burden (mediators: ESAS/HADS), or coping (mediator: Brief Cope). Although in our randomized trial, we did not identify moderators of the effect of the palliative care intervention, we will test for potential moderators to ensure generalizability of our findings, as other studies have found age and gender as moderators of the impact of palliative care in patients with lung cancer.⁶³ We will create interaction terms for the linear regression analyses and linear mixed models to examine whether differences in patient-reported QOL are moderated by patient factors (age, gender, race), transplant factors (type of HCT, conditioning intensity), or study site.

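### The Aim 3 mediation tests specify no adjustment for baseline mediator or baseline QOL, so stable differences between patients can pass for mediation if the intervention shifts the mediator

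*Combined protocol and SAP*

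**What the plan says.** Section 8.3 lists the analysis among the exploratory endpoints: "Assess whether group differences in patient-reported QOL (FACT-BMT) are mediated by improved symptom burden (mediator: ESAS/HADS), or coping (mediator: Brief Cope"). Section 10.1, Specific Aim 3, adds only the method: "We will conduct bootstrapped tests of mediation to determine whether group differences in patient-reported QOL (FACT-BMT) are mediated by improved symptom burden", with Brief Cope as the other mediator. Neither place gives a model equation, a baseline term, any other covariate, or the visits at which mediator and outcome are taken.

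Elsewhere in section 10.1 the week-2 regressions are more fully specified. For the primary endpoint (Aim 1) the comparison is made "controlling for baseline values and demographic and clinical factors (as necessary for any imbalances in baseline variables) using a linear regression model". For caregivers (Aim 2) the outcomes are compared "using linear regression models controlling for baseline values and clinical factors". The moderator tests in the Aim 3 paragraph are tied to the regression and mixed models already described. The mediation tests are not.

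The baseline data exist. The assessment paragraph just before section 9.7 says "The entire study assessment battery will be administered at all time points (except demographics) and takes approximately 20 minutes to complete", and Table 4 shows FACT-BMT, ESAS, HADS and Brief Cope at baseline.

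**The concern.** A mediation test multiplies two estimates: the effect of arm on the mediator (a) and the association of mediator with outcome given arm (b). Randomisation makes the first causal. It does nothing for the second, because patients are not randomised to their symptom or coping scores. A patient who enters more symptomatic, more distressed or coping less well can be expected to report lower FACT-BMT later, whether or not the mediator acts on QOL. If baseline scores are left out, that stable association goes into b. The bootstrap gives an interval for the product a × b but does not remove the confounding. The false discovery rate control in section 10.1 does not remove it either, since it works on p-values that are already biased.

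The conditions for the problem are ones the sponsor expects to meet. Section 1.1 reports of the previous trial: "Patients randomized to receive palliative care had a significant improvement in their QOL, symptom burden, depression, and anxiety during their hospitalization". FACT-BMT has physical and emotional well-being subscales, close in content to ESAS and HADS. Transplant type is a further possible common cause: section 9.1 says the two types recover differently, and section 9.7 assesses them on different days.

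At stake is the reading of Aim 3, one of three specific aims, which carries a directional hypothesis that coping and symptom burden mediate the effect.

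**Working it through.** **Sample size and effect (section 10.2).** The plan gives no error rate or power for mediation, so its primary power figure is reproduced to fix the inputs.

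- Patients per arm at week 2: 360 × 0.9 / 2 = 162, total 324.
- Standard error: 20 × √(2/162) = 2.222 points.
- 6.9 / 2.222 − 1.960 = 1.145, and Φ(1.145) = 87.4%. The plan states 87%, so it reproduces.
- Standardised effect on QOL: 6.9 / 20 = 0.345 SD.

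**Assumptions (not in the documents).** The true effect of mediator on QOL is zero. The intervention shifts the mediator by 0.345 SD, or by nothing. The baseline-to-week-2 correlation s and the correlation c between the stable parts of mediator and QOL (absolute value) lie between 0.3 and 0.7. Two structures were used:

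- (i) The baseline scores themselves carry all the stable information.
- (ii) Baseline and week-2 scores both measure a stable trait with error.

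**Expected bias without adjustment.** The spurious b is c × s² under (i) and c × s under (ii). The indirect effect in points is 0.345 × 20 × b = 6.9 × b, so b is also its share of the 6.9-point total effect. At 0.3/0.3 under (i) this is 0.027 × 6.9 = 0.19 points. At 0.7/0.7 it is 0.343 × 6.9 = 2.4 points under (i) and 0.49 × 6.9 = 3.4 points under (ii).

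**Simulation.** 300 trials per setting and 300 bootstrap resamples per trial, with a percentile 95% interval for a × b, with and without baseline mediator and baseline QOL in both models. Mediator shift 0.345 SD:

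| Structure | s | c | Share by formula, unadjusted | Share simulated, unadjusted | False mediation, unadjusted | False mediation, adjusted | Share simulated, adjusted |
|---|---|---|---|---|---|---|---|
| (i) | 0.3 | 0.3 | 2.7% | 2% | 6.7% | 7.3% | 0% |
| (i) | 0.5 | 0.5 | 12.5% | 14% | 57.7% | 5.0% | 0% |
| (i) | 0.5 | 0.7 | 17.5% | 18% | 78.7% | 6.0% | 0% |
| (i) | 0.7 | 0.7 | 34.3% | 35% | 89.0% | 5.7% | 0% |
| (ii) | 0.3 | 0.3 | 9.0% | 9% | 34.0% | 16.0% | 5% |
| (ii) | 0.5 | 0.5 | 25.0% | 25% | 89.0% | 33.0% | 9% |
| (ii) | 0.5 | 0.7 | 35.0% | 36% | 87.7% | 73.0% | 15% |
| (ii) | 0.7 | 0.7 | 49.0% | 48% | 84.0% | 56.3% | 12% |

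The simulation standard error at a true 5% is √(0.05 × 0.95 / 300) = 1.3 percentage points, so adjusted rates of 5-7% under (i) are compatible with 5%. In the weakest setting (first row), adjusted and unadjusted rates cannot be told apart. In the other seven, adjustment lowered the false-mediation rate, under (ii) without bringing it near 5%. The average spurious effect fell in all eight.

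**No mediator shift.** False mediation was 0-8% unadjusted and 0-3% adjusted, with an average indirect effect of about zero.

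Transplant type and site were not simulated. Their inclusion in the models rests on the design argument above.

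**The case against.** The strongest reply is that the plan is silent, not committed to an unadjusted test. A reader might infer that the sponsor has decided against adjustment, and the documents do not say that. Aim 3 asks about group differences in QOL, and the primary week-2 difference is defined with baseline adjustment. The reference to improved symptom burden could also mean change from baseline, although no change score is defined. This stands: the error rates apply only if the analyst leaves the baseline scores out.

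The contrast with Aims 1 and 2 also has a limit. Baseline adjustment is stated for their week-2 regressions only. Their mixed models use baseline as one of the time points.

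A reader might further infer that the mediation hypothesis would usually be confirmed whether or not it is true. That goes too far. The consequence needs a shifted mediator and enough stable correlation. Baseline may be taken up to two weeks before admission (section 5.1) and week 2 is placed at the symptom peak (section 9.7), so high stability cannot be presumed. The prior-trial evidence of a shift covers symptoms and mood; the documents report no effect on patients' coping.

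Nor do the results support a reading that baseline adjustment solves the problem. Measurement error leaves residual bias, and because mediator and outcome come from the same questionnaire battery, common causes at the same visit persist.

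Finally, the analysis is exploratory. That limits the stakes, but it does not make the indirect effect interpretable. Silence also leaves the covariates to be chosen after the data are seen.

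**Conclusion.** The point holds as a conditional one. The mediation tests specify no baseline adjustment. If they are run as written and the intervention shifts the mediator, false mediation lies anywhere from about the nominal rate (7%) to 89%, and the spurious indirect effect from 0.19 to 3.4 of 6.9 points by formula. Adjustment for both baseline scores brings the error to 5-7% if those scores capture the stable differences. If they measure them with error, 16-73% remains, against 34-89% without adjustment.

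These ranges rest on assumed correlations of 0.3 to 0.7, a mediator shift of 0.345 SD, 324 analysed patients and a 95% interval for each test. They show what is possible and do not predict this trial's result. The primary endpoint and its 87% power are untouched. The change is worth making before analysis because it is cheap and bears on a named aim.

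**What to change.** In section 10.1, Specific Aim 3, state that:

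- the mediator model and the outcome model both include the baseline mediator score, baseline FACT-BMT, transplant type and site, and the bootstrap is applied to the adjusted indirect effect;
- the mediator and the outcome are each taken at a named visit, and if both come from week 2 the report will say that their order in time is not established;
- a sensitivity analysis will show how strong unmeasured mediator-outcome confounding would have to be to remove the indirect effect;
- the result is reported as exploratory, with a note that baseline adjustment reduces this bias but need not remove it.

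The core change is one sentence and needs no new data: the scores are already in the baseline battery, and site and transplant type are stratification factors in section 9.1. With three sites it adds five terms to each model (two baseline scores, one for transplant type, two for site), a small number against about 324 patients. The sensitivity analysis costs some analyst time.

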8.0 Study Endpoints*

8.1 Primary endpoint:

- Compare patient QOL (FACT-BMT) scores at week 2 between the study groups

8.2 Secondary endpoints:

- Compare patients' QOL (FACT-BMT) longitudinally between the study groups
- Compare patients' symptoms (ESAS) scores between the study groups
- Compare patients' fatigue (FACT-fatigue) scores between the study groups
- Compare patients' depression and anxiety symptoms (HADS and PHQ9) between the study groups
- Compare patients' post-traumatic stress symptoms (PCL-C) between the study groups
- Compare caregivers' QOL (CARGOQOL) scores between the study groups
- Compare caregivers' anxiety and depression symptoms (caregiver HADS and PHQ9) between the study groups

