Missing Data: The analyses will initially focus on the study completers to estimate the effect of the integrated palliative care intervention in patients undergoing HCT (and their caregivers) who completed the protocol as intended without imposing assumptions about missing data. We will also use the intention-to-treat principle with all randomized subjects, conducting sensitivity analyses to explore how various assumptions about missing data and differences between completers and non-completers affect the estimated outcomes. If data appear to be missing at random, we will employ multiple imputation methods⁶⁴, maximum likelihood estimate approach with EM algorithm⁶⁵, and mixed-effects modeling⁶⁶ that can adequately account for data missing at random. However, if we find that participants do not complete the study because of disease worsening, suggesting missing data are not random, we will employ pattern mixture modeling or joint modeling approaches⁶⁷ to handle incomplete data, and perform sensitivity analysis⁶⁸ to assess the impact of missing data.

10.2 Sample Size Calculation & Power Analysis:

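### The week-2 primary comparison has no analysis set labelled primary; completers, not operationally defined, come ahead of intention-to-treat for a reason that does not hold

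*Combined protocol and SAP*

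**What the plan says.** Section 8.1 gives the primary endpoint: "Compare patient QOL (FACT-BMT) scores at week 2 between the study groups". Section 10.1, Specific Aim 1, gives the model: "The primary endpoint of the study will be to compare patient QOL (FACT-BMT) scores at week-2 between the study groups controlling for baseline values", by linear regression. Neither place says which patients enter the regression or how a missing score is handled.

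The Missing Data paragraph of section 10.1 is the only text on analysis sets. It opens "The analyses will initially focus on the study completers to estimate the effect of the integrated palliative care intervention", meaning in patients and caregivers "who completed the protocol as intended without imposing assumptions about missing data". Its next sentence begins "We will also use the intention-to-treat principle with all randomized subjects, conducting sensitivity analyses". The purpose given for the latter is "to explore how various assumptions about missing data and differences between completers and non-completers affect the estimated outcomes".

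The missing-data method then depends on a judgement about the data: "If data appear to be missing at random, we will employ multiple imputation methods", with maximum likelihood and mixed models listed beside it. Pattern-mixture or joint models come into use "if we find that participants do not complete the study because of disease worsening".

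Section 10.2 sizes the week-2 test on 10% missing at week 2 and uses 15% at 3 and 6 months. It reports 2% and 6.9% missing at week 2 and 3 months in the prior trial. Section 11.0 (Attrition Safeguards) expects a minority not to complete because of worsening health or death, and slightly more missing data than before.

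**The concern.** Three things are wrong.

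- **Labelling.** Two analysis sets are described and neither is called primary. If their results differ, the plan does not say which one answers the trial's question. As written, the efficacy result produced first comes from a group defined after randomisation.
- **Definition.** The plan describes a completer in words, but gives no assessment, visit count or time point by which one could be identified.
- **Rationale.** Restricting to completers does impose an assumption: that exclusion is unrelated to outcome, given arm and the covariates in the model. Section 11.0 expects exclusion for reasons closely tied to quality of life.

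There is a related weakness in the choice of method. Observed data cannot establish whether values are missing at random, so a method chosen on how the data appear is in effect chosen after seeing them. The paragraph also does not say whether the completers-first ordering governs the longitudinal mixed models. Those models could use every randomised patient, because section 5.1 requires the baseline questionnaire before registration and randomisation.

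**Working it through.** **1. The plan's own power.** Inputs from section 10.2: N = 360, difference 6.9, SD 20, two-sided 0.05, 10% missing at week 2.

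- Analysed: 360 × 0.90 = 324, or 162 per arm.
- Standard error: 20 × √(2/162) = 2.22.
- Noncentrality: 6.9 / 2.22 = 3.105, with 322 degrees of freedom.
- Power (noncentral t): 87.2%, matching the stated 87%.

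The sample size is therefore sound if the analysed patients are those with a week-2 score.

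**2. Bias if a completer is a patient with a week-2 score.** Let m be the missing rate by arm, g the gap in mean score between patients with and without data, and r the baseline to week-2 correlation. After baseline adjustment:

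bias ≈ (m intervention − m control) × g × (1 − r²)

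The documents give no split by arm, no gap and no correlation. I assume g = 10 to 20 points (0.5 to 1 SD) and r = 0.5 to 0.7, so 1 − r² runs from 0.75 to 0.51.

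| Missing, intervention vs control | Smallest | Largest | Share of 6.9 |
|---|---|---|---|
| Equal, same gap | 0 | 0 | 0% |
| 1% vs 3% (2% overall, as in the prior trial) | 0.02 × 10 × 0.51 = 0.10 | 0.02 × 20 × 0.75 = 0.30 | 1.5–4% |
| 8% vs 12% (10% overall, as planned) | 0.04 × 10 × 0.51 = 0.20 | 0.04 × 20 × 0.75 = 0.60 | 3–9% |

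The table shows sizes. With less loss on intervention, the bias is towards a smaller effect. Reversing the arms reverses the sign.

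**3. Hypothetical: completers limited to those who finished follow-up, or who received the protocol as intended.** Week-2 scores already collected would then be dropped.

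- Power, taking the plan's 15% rate for 3 and 6 months as a stand-in for total loss: 360 × 0.85 / 2 = 153 per arm, power 85.3%.
- Bias at an assumed 10% vs 20% loss, by the formula above at its largest: 0.10 × 20 × 0.75 = 1.5 points, so a true 6.9 would be estimated near 5.4 or 8.4 depending on which arm loses more.
- Simulation (180 per arm, all week-2 scores observed, later loss logistic in the week-2 score, baseline-adjusted regression, 2,500 runs per setting): roughly 5.3–6.4 when intervention loses 10% and control 20%, and 7.4–8.5 when reversed. At 15% in both arms the estimate is about 6.9.

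**The case against.** The strongest reply is that this is a labelling gap and little more. Section 10.1 commits without condition to an analysis of all randomised patients and to sensitivity analyses under varied assumptions, and it names suitable methods. Its opening sentence may describe only the order of work. Section 10.2 gives each time point its own missing rate, which points to a week-2 denominator for the week-2 test, and only 2% was missing at week 2 in the prior trial. A baseline-adjusted regression on observed scores is already valid if data are missing at random given the model covariates, and imputing from those same covariates would essentially reproduce it.

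Most of this stands, and it limits the size of the point. It does not say which result governs, supply a definition of completer, or make the stated rationale correct.

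A reader might go further and infer one of the following. The documents support none of them.

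- *Intention-to-treat is abandoned.* It is present; what is missing is its rank.
- *There is no criterion for completers at all.* There is one, in words; it is not operational.
- *The primary analysis is per-protocol, or limited to one-year completers.* The wording about completing the protocol, the later reference to not completing the study, and section 7.0's follow-up of about one year leave room for this. But the paragraph concerns missing data, the reference to not completing the study explains why data may be missing, and section 10.2's rates by visit count against it.
- *The primary estimate will be badly biased.* At week 2 that needs a split such as 5% vs 15%, which gives 0.5 to 1.5 points (0.10 × 10 × 0.51 to 0.10 × 20 × 0.75). No passage suggests such a split.

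**Conclusion.** The point holds as a narrow defect in the analysis plan that should be corrected before the data are analysed. No set is labelled primary for the week-2 regression, completer cannot be applied as defined, and the claim of avoiding assumptions is false.

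On the likeliest reading the numerical consequence is probably small: zero with equal loss and equal gaps, and otherwise about 0.1 to 0.6 points, against a standard error of 2.22. Every arm split, gap and correlation behind those figures is assumed. The range of roughly 5.3 to 8.5 for a true 6.9 belongs only to the hypothetical reading with an assumed 10% vs 20% loss. It shows that bias could run in either direction and is not an expected effect. The sample size and the stated 87% power are not in question.

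**What to change.** 1. Name as primary all randomised patients in their assigned arm. Use every observed week-2 FACT-BMT score, regardless of visits received, palliative care received by controls, or later follow-up.
2. Fix in advance one missing-at-random method for the primary analysis: a likelihood model, or multiple imputation with auxiliary variables already collected, such as baseline ESAS, HADS and PHQ-9, the comorbidity index and transplant type. Remove the step that chooses the method on how the data appear.
3. Run one named not-at-random sensitivity analysis, such as a pattern-mixture or delta-adjusted model, whatever the apparent reason for dropout.
4. Define completer with a time point, and label that analysis supportive.
5. Delete the phrase claiming that no assumptions about missing data are imposed.
6. Apply the same ordering to the longitudinal patient models.

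The cost is a few sentences and slightly more analysis work. Sample size and data collection do not change, and the main methods are already named in section 10.1.
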